3.5.2 Baseline Definitions

For Period 1, Baseline for safety and in-clinic assessments is defined as the most recent measurement prior to the first administration of study treatment.

For in-clinic efficacy parameters including change from baseline measurements at post-Randomization timepoints, Baseline is the last Clinic BP measurement occurring prior to the first dose with randomized study treatment.

Baseline for home SBP measurements is defined as measures taken during the week prior to Randomization,

with derivation defined in Table 3-3.

3.5.3 Study Period for Analysis

The study is planned with 4 periods (Section 2.2.3) with varying treatment assigned in both trial medication and dose level during the specified periods. For a minority of participants, Follow-Up visits 1 and 2 may not occur at 6 and 12 weeks, respectively and screening visit is not always 4 weeks before baseline visit, due to protocol-specified visit windows and IMP supply interruptions. Therefore, the analysis periods will be defined:

- Period 1: From Week -4 to Randomization, defined as from screening to Randomization and Baseline Visit,
- Period 2: From Randomization to Week 6, defined as from Randomization and Baseline Visit to Followup Visit 1,
- Period 3: From Week 6 to Week 12, defined as from Follow-up Visit 1 to Follow-up Visit 2,
- Randomized Period: From Randomization to Week 12, defined as from Randomization and Baseline Visit to Follow-up Visit 2 (Period 2 and Period 3),
- Period 4: From Week 12 to Week 16, defined as from Follow-up Visit 2 to end of study (Week 16).

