2.2.3 Trial design

The trial design is described in detail in Section 7 of the protocol, with the following figure summarising the overall design:

0				-	-	
		Period 1	Period 2	Period 3	Period 4	
		Single-blind run-in	Double-blind	Double-blind	Safety FU]
Screening		GMRx2 Dose 2	GMRx2 Dose 2 T 20 / A 2.5 T 20 / I 1.25 A 2.5 / I 1.25	GMRx2 Dose 3 T 40 / A 5 T 40 / I 2.5 A 5 / I 2.5	Non-trial treatment	
Visit	RI	F	۲ F	5U1 F	02	EOT
Visit No.	V1	V	/2	V3	V 4	V5
Week	-4		0	6	12	16

GMRx2 Dose2 = T 20 / A 2.5 / I 1.25; GMRx2 Dose3 = T 40 / A5 / I 2.5; T = telmisartan; A = amlodipine; I = indapamide; RI = run-in; R = randomization; FU = follow-up; EOT = end of trial; V = visit; Forced up-titration at FU1; EOT will be telephonic.

Of particular note are the two study visits Week 6/Follow-up 1 (FU1) and Week 12/Follow-up 2 (FU2). Preceding both visits, participants will be requested to perform extra home BP measurements in the week running up to the clinic visit. At FU1, all participants are expected to be up-titrated to the higher level of study drug, unless there is a specific contraindication, such as symptomatic hypotension. At FU2, the participant will complete the double-blinded part of the trial and continue on non-trial treatment in a safety follow-up period. Although time periods have been nominated (6 weeks for FU1 and 12 weeks for FU2) these are indicative only and actual time periods may vary within an expected window, as specified within the study protocol.

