3.11 Analysis of Safety Outcomes

3.11.1 Adverse Events of Special Interest

3.11.1.1 Definitions & Derivations

An Adverse Event (AE) is any undesirable medical event occurring to a subject in a clinical trial, whether or not related to the trial medications.

Drug-related AEs are AEs with a causality to drug being possibly, probably, definitely related or with a missing causality.

The only non-serious Adverse Events to be recorded are Adverse Events of Special Interest (AESIs). An AESI is the subset of AEs that are due to:

- Dizziness or any other symptom or event possibly related to hypotension,
- Abnormality detected in laboratory assessments of sodium, potassium, uric acid, glucose, lipids, creatinine or eGFR,
- Symptom of pedal edema reported by the participant,
- Any other symptom or laboratory abnormality that led to treatment withdrawal.

AESI include events occurring during Run-in, Randomization Period, and Follow-up.

A Serious Adverse Event (SAE) is any AE that meets one or more of the following criteria:

- Results in death;
- Is life-threatening;
- Requires in-patient hospitalization or prolongation of existing hospitalization;
- Results in persistent or significant disability/incapacity;
- Results in a congenital anomaly/birth defect.

Important medical events that may not result in death, be life-threatening, or require hospitalization may be considered serious when, based upon appropriate medical judgment, they may jeopardize the patient or subject and may require medical or surgical intervention to prevent one of the outcomes listed in this definition.

AESIs and SAEs will be recorded from time of informed consent up to 30 days after trial medication discontinuation.

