3.11.1.2 Adverse Event Summaries

For the summary of safety parameters, AEs will be classified according to the treatment period and treatment received as of the start date of the AE (Section 3.5.3). If an AE is ongoing at the time of randomization, it will be allocated to the Period 1 treatment. If a treatment ongoing at randomization worsens following randomization, the AE worsening will be allocated to the Period 2 treatment.

AESIs and SAEs will be classified according to the MedDRA (Medical Dictionary for Regulatory Activities) system (version 24.0, March 2021) and summarized by system organ class and preferred term.

Treatment periods for AE summary include: Period 1, Period 2, Period 3, Randomization Period, and Period 4. The total number of events and incidence of participants experiencing AESIs will be tabulated by treatment group and overall for the specified study periods.

For each period, any AESI or SAEs that emerges or worsens during the period of interest will be summarized:

- Adverse Events of Special Interest,
- Serious AE,
- Related AESIs defined as those judged by the investigator to be 'possibly', 'probably' or 'definitely' related
- Related SAEs defined as those judged by the investigator to be 'possibly', 'probably' or 'definitely' related,
- AE leading to trial medication discontinuation
- AE leading to trial discontinuation defined as a request by the participant to withdraw from future follow-up visits

AESIs of abnormality detected in laboratory assessments for Period 1 will only include those whose lab value for that parameter was in the normal range at baseline. Summaries of AESI and SAEs occurring during the Randomized Period will include risk differences with 95% CI, computed using the Newcombe hybrid score method (with continuity correction; https://pubmed.ncbi.nlm.nih.gov/21996567/), to evaluate GMRx2 against each dual control treatment group and overall. System organ classes and preferred terms with events occurring in at least 1% of the sample will be included.

In addition, the frequency and percentage of participants discontinuing treatment due to an AE will be reported with risk differences between treatment groups computed using the Newcombe hybrid score method (with continuity correction) to evaluate the primary safety endpoint among GMRx2 treatment participants compared to each dual control treatment group, and overall.

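### SAP 3.5.3 starts Period 1 at screening, up to 14 days before the first run-in capsule, so AESIs and SAEs that precede any dose can be counted in the GMRx2 run-in tables (minor)

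*SAP*

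**What the plan says.** SAP 3.5.3 sets the analysis periods. The first is "Period 1: From Week -4 to Randomization, defined as from screening to Randomization and Baseline Visit".

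SAP 3.11.1.1 sets the recording window: "AESIs and SAEs will be recorded from time of informed consent up to 30 days after trial medication discontinuation".

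SAP 3.11.1.2 then gives the allocation and tabulation rules:

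- Allocation: "AEs will be classified according to the treatment period and treatment received as of the start date of the AE (Section 3.5.3").
- Periods available: "Treatment periods for AE summary include: Period 1, Period 2, Period 3, Randomization Period, and Period 4".
- Events counted, for each period: "any AESI or SAEs that emerges or worsens during the period of interest will be summarized".
- Carry-over: "If an AE is ongoing at the time of randomization, it will be allocated to the Period 1 treatment".
- A filter for laboratory AESIs only: those from "laboratory assessments for Period 1 will only include those whose lab value for that parameter was in the normal range at baseline".

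On timing, footnote 10 of the schedule of assessments (Protocol Table 5, repeated in SAP Appendix 3) places screening 0 to 14 days before run-in starts. Protocol 10.3.2 explains how a gap arises. Laboratory results must be reviewed before run-in medication starts, and a participant whose results are pending may come back for the capsules or have them couriered.

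Elsewhere the SAP treats Period 1 as the run-in itself. The figure in 2.2.3 shows Screening ahead of Period 1, which is headed "Single-blind run-in". Sections 3.4.2 and 3.5 also equate Period 1 with the run-in. P1 Day 1 (3.5) and the Period 1 safety baseline (3.5.2) are both tied to the first dose.

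**The concern.** Run-in SAEs by severity and system organ class are a planned descriptive output (Protocol 9.2.3), and SAP 3.11.1.2 adds AESI tables for the same period. A reader will take these tables as experience on GMRx2 Dose 2, since SAP 3.5 gives every participant in Period 1 the planned treatment GMRx2.

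If Period 1 opens at screening, the window can include days on which no GMRx2 had been taken. Participants may enter on up to three BP-lowering drugs (Protocol 8.2.1), so dizziness in that gap could reflect earlier treatment and still appear under GMRx2. The Safety Set does not prevent this. It removes people who were never dosed, but not the pre-dose events of people who were dosed later. At stake are the accuracy of the run-in tables and whether two programmers would produce the same ones.

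**Working it through.** The plan states no figure on this point that could be reproduced. The check has three parts: trace one event through the rules, measure the untreated window, and illustrate the count.

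**1. Tracing one event.** Take a participant screened 14 days before the first capsule (P1 Day -14), with dizziness starting on P1 Day -7, who is then dosed.

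| Rule | Result for this event |
|---|---|
| Recording from consent (3.11.1.1) | Recorded |
| Safety Set (3.4.2) | Participant included |
| Period by date (3.5.3) | Period 1 |
| Event emerges in the period (3.11.1.2) | Counted in Period 1 |
| Treatment received at event start (3.11.1.2) | None, so not GMRx2 |
| Period for events with no treatment (3.11.1.2) | None listed |
| Normal-baseline filter (3.11.1.2) | Does not apply to symptoms or SAEs |

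The date rules count the event and the treatment rule does not. No sentence says which prevails. The negative relative day would show in a listing, but no rule uses it to keep the event out of a table. The abbreviation list contains terms for treatment-emergent events, but the SAP text never defines or applies them.

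**2. Untreated share of the Period 1 window.** Share = gap / (gap + run-in). Run-in lengths are 21 days (minimum) and 28 days (ideal) from Protocol 10.3.2, and 35 days (maximum) from Table 5, footnote 11. At the 14-day maximum gap:

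- 28-day run-in: 14 / 42 = 33%
- 21-day run-in: 14 / 35 = 40%
- 35-day run-in: 14 / 49 = 29%

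With no gap the share is 0%. These figures describe one participant's window. They are not an error rate for the tables.

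**3. Illustrated count.** Expected participants = 2000 × share with a gap × event proportion × gap days / 182.

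Inputs:
- 2000 dosed in run-in, from the Protocol 12.3 expectation of at least 2000 entering.
- Event proportions from the usual-care arm of the earlier open-label triple-pill trial (Protocol 5.4): SAE 6.0%; dizziness, presyncope or syncope 2.8%. Reading these as 6-month figures (182 days) at a constant rate is an assumption.
- Share with a gap of 5%, 10% or 25%, and gap length of 7 or 14 days. The shares are assumptions. SAP 3.5.3 speaks only of a minority with off-schedule visits, and that sentence also covers the two follow-up visits.

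| Event | Gap | 5% share | 10% share | 25% share |
|---|---|---|---|---|
| SAE | 7 days | 0.23 | 0.46 | 1.15 |
| SAE | 14 days | 0.46 | 0.92 | 2.31 |
| Dizziness etc. | 7 days | 0.11 | 0.22 | 0.54 |
| Dizziness etc. | 14 days | 0.22 | 0.43 | 1.08 |

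Worked extremes:
- SAE, lowest: 2000 × 0.05 × 0.06 × 7/182 = 0.23
- SAE, highest: 2000 × 0.25 × 0.06 × 14/182 = 2.31
- Dizziness, lowest: 2000 × 0.05 × 0.028 × 7/182 = 0.11
- Dizziness, highest: 2000 × 0.25 × 0.028 × 14/182 = 1.08

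For scale, the same rates over a 28-day run-in in all 2000 give 2000 × 0.06 × 28/182 = 18.5 participants with an SAE and 2000 × 0.028 × 28/182 = 8.6 with dizziness, presyncope or syncope.

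**The case against.** The strongest reply is that the SAP already excludes these events. Allocation depends on treatment received as well as period, nothing has been received before the first capsule, and SAP 3.4.2 analyzes safety by actual treatment. Section 3.5 separates pre-treatment from on-treatment days, and the schedule gives screening and run-in start the same nominal week and day. On this view, screening in 3.5.3 is shorthand for the Week -4 visit that opens the run-in. An event can also fall outside every table without a named category: consent may be taken before screening, so some recorded events already precede all the 3.5.3 periods.

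Much of this stands as evidence of what was intended. It does not settle the text. Section 3.5.3 itself notes that screening is not always 4 weeks before baseline and still starts the period there, and the rule for what each period's tables count has no dosing condition.

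Three further points for the other side also stand:

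- The sentence on events ongoing at randomization mainly decides between Period 1 and Period 2. It adds little to the case beyond setting no limit on when the event began.
- Laboratory AESIs are largely protected by the normal-baseline filter, and discontinuation for an adverse event generally presupposes dosing.
- The SAE illustration ignores that many people with a serious event in the gap would never be dosed. Eligibility must be confirmed before run-in medication starts, and stroke, acute coronary syndrome and illness judged a significant risk are exclusions. The true count is therefore likely to be lower.

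A reader might go further and infer that the SAP plainly assigns pre-dose events to GMRx2. The documents do not support that, because the treatment-received condition is a genuine competing reading.

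**Conclusion.** The point holds as a minor one: the wording of 3.5.3 is wrong as it stands. It conflicts with the SAP's own use of Period 1 as the run-in, and 3.11.1.2 has no pre-treatment category to resolve the conflict. That events can be counted is clear from the text. That any will be miscounted is less certain, since a programmer might follow the treatment-received condition.

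The effect is probably at most one or two participants. This is an upper illustration that rests on the assumed gap shares, the borrowed event rates and their 6-month reading. The documents do not allow an actual count.

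A reader might infer that up to a third of run-in events are misattributed, from the 14/42 window share, or that the randomized safety results are biased. Neither follows. The window share applies only to a participant with the longest gap and a 28-day run-in. The randomized comparisons and the primary safety endpoint start at randomization. Only the descriptive, single-arm run-in tables are affected, and any error adds events to GMRx2, so it does not flatter the product.

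**What to change.** - In SAP 3.5.3, add: *For adverse-event summaries, Period 1 starts at P1 Day 1 (first single-blind dose).*
- In SAP 3.11.1.2, add: *AESIs and SAEs that start from consent to the day before P1 Day 1 are pre-treatment. They are listed, and are not counted in the Period 1 tables unless they worsen on or after P1 Day 1.*
- In the same section, make the sentence on events ongoing at randomization subject to that rule.

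This also gives a place to events between an early consent and screening. The cost is three SAP sentences and one listing. First-dose dates are already needed for P1 Day 1, so no new data are required. The only downside is that Period 1 counts may fall slightly.

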3.6 Subject Disposition

All participants screened who met study inclusion criteria for Period 1 (active run-in) will be accounted for. The number of participants who were randomized; and reasons for exclusion for non-randomized participants will be summarized.

Subject disposition will be tabulated for the following categories and will include all participants in the Screened Set:

- Number (%) of participants screened
- Number (%) of participants entered run-in period
- Number (%) of participants randomized
- Number (%) of participants randomized, ineligible for randomization
- Number (%) of participants randomized but did not receive study treatment
- Number (%) of participants completing Period 2 (defined as attending Week 6, Visit FU1)
- Number (%) of participants completing Period 3 (defined as attending Week 12, Visit FU2)
- Number (%) of participants completing the trial, including safety follow-up (defined as attending Week 12, Visit FU2 and Week 16, Visit EOT)
- Number (%) of participants prematurely and permanently discontinuing the trial medications and reasons
- Number (%) of participants prematurely and permanently discontinuing from the trial and reasons
- Number (%) of participants in each analysis population (Section 3.4).

3.7 Baseline Characteristics

Description of the participant baseline characteristics will be presented by treatment group and overall. Baseline characteristics will be summarized on the Safety Set by treatment group, Safety Set by Randomization Eligibility and Randomized Set by treatment group, including the below parameters:

- Demographic characteristics: age (years), sex, race, ethnicity, height (cm), weight (kg), BMI (kg/m²), country/region, education
- Lifestyle: Smoking status and alcohol consumption
- 12-lead ECG: Interpretations will be tabulated

• Screening visit number of prior BP medications

The following parameters will be summarized:

- Demographic characteristics, lifestyle, and 12-lead ECG
- Screening visit clinic BP (SBP and DBP)
- Average home BP at Randomization (last week of Period 1 SBP) (see Section 3.10.2 for derivations)
- Change in clinic BP from Screening Visit to Randomization visit
- Change in home BP from 1st to last week of Period 1 will be summarized by Randomization Eligibility

Medical history will be provided in by-participant data listings. Summaries may also be presented.

3.8 Prior/Concomitant Medications

Prior and concomitant medications will be summarized by treatment group. Prior medications are medications that were being taken at the time of screening. Concomitant medications are medications that started or were ongoing from run-in period to the end of trial. Concomitant medications will be summarized separately for medications taken during Period 1 (pre-Randomization) and post-Randomization.

Prior/Concomitant medication will be summarized using descriptive statistics:

- Number (%) of participants with at least one prior medication, by ATC code level 1 and preferred term
- Number (%) of participants with at least one concomitant medication during Period 1, by ATC code level 1 and preferred term
- Number (%) of participants with at least one concomitant BP lowering medication during Period 1, by ATC code level 1 and preferred term
- Number (%) of participants with at least one concomitant medication post-Randomization, by ATC code level 1 and preferred term
- Number (%) of participants with at least one concomitant BP lowering medications postrandomization, by ATC code level 1 and preferred term

Concomitant medications will be summarized by Anatomical Therapeutic Chemical (ATC) term according to the WHO Drug Dictionary (WHO DD) (March 2021 version or later if up-versioning occurs) used for drug coding (https://www.whocc.no/atc_ddd_index/).

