10.2.11. Allocation of Trial Medication

During the single-blind run-in period (Week -4 to Week -1 inclusive) all participants will be allocated GMRx2 dose version 2. During the double-blind period (Week 1 to Week 12 inclusive) all participants will be allocated GMRx2 or one of the three dual combinations as per the randomization scheme. Neither the site staff nor the participants will have foreknowledge of the treatment allocation at randomization. After the completion of the double-blind treatment period at Week 12, participants will be switched to non-trial medication as per local guidelines/practice.

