10.3.9. Week 16 visit (End of Trial Visit)

- Contact participant by telephone.
- Record AESIs or SAEs since the previous visit.
- Review all medications being taken by the participant and update medications
- Explain that the trial follow-up is now completed and thank participant

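### SAP 3.8 tabulates concomitant BP-lowering drugs by arm in one window from randomization to Week 16, so add-on use before the Week 12 reading is mixed with routine post-trial prescribing and any between-arm difference is diluted.

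*SAP*

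**What the plan says.** SAP 3.8 sets the window: "Concomitant medications are medications that started or were ongoing from run-in period to the end of trial". It divides that window once: "Concomitant medications will be summarized separately for medications taken during Period 1 (pre-Randomization) and post-Randomization". Reporting is by arm: "Prior and concomitant medications will be summarized by treatment group". Two tables concern BP-lowering drugs. One covers Period 1. The other covers everything after randomization: "Number (%) of participants with at least one concomitant BP lowering medications postrandomization, by ATC code level 1 and preferred term".

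Protocol 10.2.11 says what happens at Week 12: "After the completion of the double-blind treatment period at Week 12, participants will be switched to non-trial medication as per local guidelines/practice". SAP 2.2.3 likewise labels Period 4 as non-trial treatment. Protocol 10.3.9 makes Week 16 the end-of-trial contact and lists among its tasks: "Review all medications being taken by the participant and update medications".

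Protocol 8.6 allows open-label telmisartan and/or amlodipine on top of blinded medication when BP is high. SAP 3.5.3 defines both a Randomized Period (randomization to Follow-up Visit 2, FU2) and a Period 4 (FU2 to Week 16). SAP 3.8 uses neither.

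**The concern.** The primary analysis follows a treatment-policy strategy (SAP 3.10.1.1), and add-on BP treatment is not among its four listed intercurrent events. Home readings taken on add-on therefore stay in the comparison. To interpret the mean differences and control rates, a reader needs to know how much open-label treatment each arm had received by the Week 12 reading. Protocol 12.3 also assumes drop-in and drop-out similar to that in earlier triple-versus-dual trials, and the drop-in part can be checked only against add-on use before Week 12.

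The post-randomization table in SAP 3.8 is the natural place for this information. Because its window continues past the switch at Week 12, it also counts drugs that play no part in the randomized comparison.

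**Working it through.** The plan states no figure for this table, so there is none to reproduce. The check sets the texts side by side and then works out the dilution.

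**1. Where the window ends.** SAP 3.8 runs to the end of trial. Protocol 10.3.9 places that at Week 16, and medications are updated at that contact. Drugs started in Weeks 12 to 16 therefore fall in the post-randomization window.

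**2. Whether another summary isolates add-on.**
- SAP 2.3.3 names add-on treatment among the possible changes to medication, but plans no table of it.
- It is not a disposition category (SAP 3.6), a named major-deviation category (SAP 3.9.3) or an intercurrent event (SAP 3.10.1.1).
- SAP 3.5 separates Period 1 from what follows, but for efficacy and safety summaries, and it does not clearly split the randomized period from follow-up.

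**3. Dilution.** Let a and b be the true proportions with add-on before Week 12 in GMRx2 and in a dual arm. Let s be the proportion with a BP drug recorded after Week 12, equal across arms and independent of add-on. The table shows

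- GMRx2: a + (1-a)s
- dual: b + (1-b)s
- difference: (b-a)(1-s)

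Only the share among participants without add-on enters these formulas. Independence lets s be read as the share in the whole arm.

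Two illustrations follow. The first uses assumed rates of 2% v 5%. The second borrows the additional-medication rates by 12 weeks in the quadruple quarter-dose trial described in Protocol 5.5: 44/300 = 14.7% v 115/291 = 39.5%. That trial compared the combination with monotherapy, so its rates are not a forecast for this one.

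| s | 2% v 5%: shown | difference (points) | 14.7% v 39.5%: shown | difference (points) |
|---|---|---|---|---|
| 0 (cut at FU2) | 2.0 v 5.0 | 3.0 | 14.7 v 39.5 | 24.9 |
| 0.50 | 51.0 v 52.5 | 1.5 | 57.3 v 69.8 | 12.4 |
| 0.90 | 90.2 v 90.5 | 0.30 | 91.5 v 94.0 | 2.5 |
| 0.95 | 95.1 v 95.25 | 0.15 | 95.7 v 97.0 | 1.2 |
| 1 | 100 v 100 | 0 | 100 v 100 | 0 |

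For example, at s=0.95: 0.02 + 0.98 x 0.95 = 0.951 and 0.05 + 0.95 x 0.95 = 0.9525, a difference of 0.0015, which equals 0.03 x 0.05.

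**4. Preferred-term rows.** Telmisartan and amlodipine can be recorded as add-on (Protocol 8.6), as open-label cover when Period 3 supply fails (Protocol 15) or as post-trial care under local practice (Protocol 10.2.11). One row can hold all three uses, so these rows are diluted too, though by the share taking that drug for another reason rather than by the whole of s. ATC level 1 is too coarse to separate classes of BP drug.

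**The case against.** The strongest reply is that this is a descriptive table: it changes no estimate, test, analysis set or imputation rule. If add-on were commoner in the dual arms, it would usually pull the treatment-policy difference toward zero, so the missing breakdown would not flatter GMRx2. That stands, and it limits the point to reporting.

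Table shells are mentioned in the SAP revision history but are not in the documents, so a Week 12 split there cannot be excluded. SAP 3.5 also requires a relative study day in dated listings. A participant-level listing is not a summary by arm, however, and the SAP text governs what is planned.

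Two stronger readings are tempting.

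- A reader might infer that the table hides every difference between arms, with near-100% use everywhere. That would need s at or close to 1. The documents describe the switch at Week 12 but give no rate of recorded BP drugs afterwards, and Protocol 8.9 speaks only of appropriate continued care. What they support is dilution. Preferred-term rows may keep some information.
- A reader might extend the point to run-in, because SAP 3.5.3 has "Period 1: From Week -4 to Randomization, defined as from screening to Randomization and Baseline Visit", so that drugs stopped for run-in would count as concomitant. SAP 3.8 has its own rule, starting at run-in, and treats drugs taken at screening as prior. Protocol 10.2.14 requires non-trial BP drugs to be stopped before trial medication starts. At most, two descriptions of when the window opens could be aligned. Add-on during run-in also bars randomization (Protocol 8.6), so it cannot affect the comparison between arms.

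**Conclusion.** The point holds as a fault in a planned summary. As written, the one post-randomization table of BP-lowering drugs by arm combines use before the Week 12 reading with treatment after it, and nothing else in the SAP text recovers the first part. A true difference in add-on use is shrunk by (1-s). In the 2% v 5% illustration it falls from 3.0 points to 0.15 at s=0.95 and to 0 at s=1. The size rests on assumed add-on rates, an assumed s, equality of s across arms and independence. That the window mixes the two kinds of use rests on the text alone.

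The primary estimate and its test are unaffected. What is lost is the reader's view of drop-in by arm behind a treatment-policy result, and a check on the drop-in assumption in Protocol 12.3. The change should be made because it is cheap and the periods it needs are already defined.

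**What to change.** In SAP 3.8, replace the single post-randomization window for BP-lowering drugs with two tables by arm:

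1. First randomized dose to FU2, with Periods 2 and 3 as defined in SAP 3.5.3 shown separately, excluding drugs started at FU2 as post-trial care.
2. Period 4, on its own.

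Within the first table, show add-on under Protocol 8.6 separately from open-label treatment for supply interruption (Protocol 15) and from alternative treatment after early discontinuation (Protocol 8.8), as far as the recorded data allow. Dates alone will not separate these uses. If the reason for use was not recorded, say so in a footnote. Counts and percentages are enough; no added between-arm tests or risk differences are needed.

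The cost is a few lines of SAP text and a re-cut of one table into two. The SAP's own definition, which turns on whether a drug started or was ongoing in a window, already presupposes start and stop timing for concomitant drugs. The documents do not list those eCRF fields, so their availability should be confirmed.
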